9.3 Statistical Methods

General considerations: we will incorporate standard techniques such as omnibus tests and appropriate adjustments to significance (α) levels (*e.g.*, Bonferroni correction) for *post-hoc* contrasts to control for multiple comparisons. Both selection and attrition biases might occur. Appropriate techniques (*e.g.*, Heckman 2-stage approach (GEE Probit Model)^{254;255} and Monte Carlo (EM algorithm)²⁵⁶ will be used to address biases or missing data. Attributes of those who withdrew to follow-up will be contrasted with completers to determine sources of attrition biases. Since only two time points will be analyzed, we will use linear regression models with the annual rate of amyloid change as dependent variable. Significance will be defined by $p < .05$ where p will be Bonferroni corrected when testing *post-hoc* contrasts.

- **Hypothesis (1)**: H1.1) for %AF associations, linear regression models, with each of SWS characteristics as the dependent variable, will be regressed on %AF controlling for age, sex, BMI, AHI, TST, sleep efficiency and WASO. H1.2) This model will test interaction by including the best SWS predictor as dependent variable, the psychosocial factor as a classification factor, %AF and the term created as the cross product of psychosocial factors and %AF.
- **Hypothesis 2-3 (H2-3)**: First we will calculate the associations between race and AD_{PiB}mask represented both as binary (AA *vs.* white) and numeric (%AF). Further analyses will use the representation (s) of race significantly associated with amyloid burden. Second, we will use hierarchical

CONFIDENTIAL

linear regression, with rate of change of AD_{PiB}mask as the dependent variable and race as independent, adjusting for the matching factors: age, sex, BMI, education and annual income (block 1); ApoE4 and ABCA7 (block 2); DWML volumes, DKI indices and mPFC volume (block 3); and SWS characteristic (*e.g.* relative SWA) (block 4). Other covariates (*e.g.*, psychosocial) will be included in the final models if significantly different between AAs and whites as indicated by unequal variance t tests. Although we anticipate that relative SWA will be the best predictor of longitudinal change in AD_{PiB}mask, the best fitting model will be then replicated with each of the other SWS characteristics not listed before. On a final step, we will test whether the effect of SWS on amyloid deposition is different (*i.e.*, stronger) among AAs. The model would include AD_{PiB}mask change, the binary indicator of race (AA=1 *vs.* white=0) and SWA as described in H1.2. If the interaction is significant, it will imply that the effect of SWA on amyloid varies as a function of race. The sign of the estimated coefficient for this term would indicate whether SWA has a significantly stronger or weaker effect among AA. Exploratory Hypothesis: cognitive z-score change in subjects that show improvement in maze CT will be compared with those that don't show improvement using ANCOVA controlling for age, sex, BMI, race, education and ApoE4 status.

- **Post-hoc analyses**: a subset of *post-hoc* analyses will be performed by controlling by PiB levels at baseline and by splitting the sample into PiB+ and PiB- at baseline and performing a separate analysis for each subset. Stratified analyses will also be performed for men and women, as well as for AAs and whites. In addition, we will formally test the impact of PiB status (defined as PiB SUVR \geq 1.4) on the association of sleep measures with longitudinal increases in AD_{PiB}mask. Although we do not anticipate that sleep or SWS characteristics will change over the follow-up period, *post-hoc* analyses will be performed by assessing longitudinal changes in the sleep measures as correlates and predictors of longitudinal changes in the outcomes measures, using paired sample t-tests to assess the change in outcomes and sleep.

10 Source Documents and Access to Source Data/Documents

Source data is all information, original records of clinical findings, observations, or other activities in a study necessary for the reconstruction and evaluation of the study. Source data are contained in source documents. Examples of these original documents, and data records include: hospital records, clinical and office charts, laboratory notes, memoranda, subjects' diaries or evaluation checklists, pharmacy dispensing records, recorded data from automated instruments, copies or transcriptions certified after verification as being accurate and complete, microfiches, photographic negatives, microfilm or magnetic media, x-rays, subject files, and records kept at the pharmacy, at the laboratories, and at medico-technical departments involved in the study.

The study case report form (CRF) is the primary data collection instrument for the study. All data requested on the CRF must be recorded. All missing data must be explained. If a space on the CRF is left blank because the procedure was not done or the question was not asked, write "N/D". If the item is not applicable to the individual case, write "N/A". All entries should be printed legibly in black ink. If any entry error has been made, to correct such an error, draw a single straight line through the incorrect entry and enter the correct data above it. All such changes must be initialed and dated. DO NOT ERASE OR WHITE OUT ERRORS. For clarification of illegible or uncertain entries, print the clarification above the item, then initial and date it.

Access to study records will be limited to IRB-approved members of the study team. The investigator will permit study-related monitoring, audits, and inspections by the IRB/EC, the sponsor, government regulatory bodies, and University compliance and quality assurance groups of all study related documents (*e.g.* source documents, regulatory documents, data collection instruments, study data etc.). The investigator will ensure the capability for inspections of applicable study-related facilities (*e.g.* pharmacy, diagnostic laboratory, etc.).

Participation as an investigator in this study implies acceptance of potential inspection by government regulatory authorities and applicable University compliance and quality assurance offices.

CONFIDENTIAL

11 Ethics/Protection of Human Subjects

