3.1 Primary Objective

Aim 1 will test if African ancestry (%AF) is associated with short SWS duration and poor SWA in older AAs. **Challenge:** AAs consistently spend less time in SWS than whites²³⁻³². Although SWS shows significant heritability, social stressors may moderate these differences. **Approach:** test whether %AF⁴⁰ is associated with SWS characteristics after controlling for psychosocial factors (*e.g.* stress related to ethnicity). **Outcome:** positive results would suggest that racial differences in SWS have genetic underpinnings.

Aim 2 will test the effect of race and its interaction with baseline short SWS duration/poor SWA on longitudinal amyloid deposition. **Challenge:** AAs spend less time in SWS²³⁻³², a sleep stage important for A β dynamics⁴¹⁻⁴³ that may confer protection against amyloid deposition⁴⁴. **Approach:** assess how race is associated with longitudinal PiB uptake and its interaction with short SWS duration and poor SWA, after controlling for: 1) medial prefrontal (mPFC) atrophy, TST, AHI4% and cerebrovascular damage (measured as white matter lesion [WML] volume and abnormal diffusion kurtosis imaging [DKI] indices); and, 2) psychosocial factors, health care behaviors and medical morbidity. **Outcome:** reduced SWS/SWA would become a novel risk factor for AD in African Americans (AAs).

Aim 3 will test the effect of race and baseline poor SWA on cognition. **Challenge:** race and poor sleep have been associated with cognitive impairment. However, most studies are confounded by the inclusion of OSA patients, subjective measurements of sleep, lack of valid cognitive assessments for AAs and inadequate enrollment of minorities. **Approach:** we will test for the association between race and longitudinal changes in global cognition, memory, executive function and a sleep-dependent spatial navigational memory task. In addition, we will test their interaction with baseline SWA, using a similar approach as in Aim 2. **Outcome:** positive results would emphasize the importance of health messages promoting good sleep hygiene among AA elderly.

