9.1 Study Hypotheses

1. Hypothesis 1.1: poor SWS characteristics (short SWS duration, low %SWS, low relative SWA, low SWS continuity and high AI) at baseline will be associated with high %AF. Hypothesis 1.2: psychosocial factors (*e.g.* perceived discrimination) will partially moderate the above relationships.
2. Hypothesis 2.1: race will be associated with longitudinal increases in the annual rate of AD_{PiB}mask change. Hypothesis 2.2: the effect of race in terms of longitudinal increases in AD_{PiB}mask will be partially explained by poor relative SWA at baseline.
3. Hypothesis 3.1: race will be associated with longitudinal changes in global cognition, memory, executive function and sleep-dependent spatial navigational memory. Hypothesis 3.2: the association of race in terms of cognitive decline will be partially explained by poor relative SWA at baseline. Exploratory Hypothesis: absence of improvement in sleep dependent memory consolidation at baseline will be associated with longitudinal decreases in global cognition, memory and executive function.

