9.2 Sample Size Determination

Power was assessed under the assumption that dropout replacement will allow complete data to be acquired from 200 subjects. Based on the existing literature²³⁻³², the coefficient of variation (CV) of SWS duration is anticipated to be as high as 90% among AA and 40% among whites. Baseline data from 150 AA and 60 whites will therefore provide 80% power at the 5% significance level to detect a mean SWS duration among whites that is at least 28% higher than among AA. Based on PD4, the CV of PiB uptake at baseline is anticipated to be as high as 35% among AA and 25% among whites, providing 80(90)% power at the 5% significance level to detect a mean PiB uptake among AAs that is at least 13%(15%) higher than in whites. For Aim 1, the study will have 80% power at the 5% significance level to detect correlations of magnitude $|r|=0.20$ (the study from Halder et al³⁹ showed an R^2 of 11, implying an even greater correlation of 0.33 can be expected in our study). The multivariable regression analysis will have 80% power to detect SWS characteristics that can explain 3% of the variance in the longitudinal change in AD_{PiB}mask (Aim 2) or cognition (Aim 3) after adjusting for covariates that together explain at least 25% of the variance in AD_{PiB}mask/cognition. The detectable effect of 3% variance explained, implies the study can detect partial correlations of magnitude 0.1 between SWS and the outcomes adjusted for the cofactors. It is noted that the power of the multivariable analyses will improve if the covariates explain >25% of the variance. The study will have 80% power to detect sleep measures that explain 10% of the variance in the AD_{PiB}mask ratio even if the covariates explain a negligible percentage of the variance.

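### Section 9.3 does not carry out the adjustment stated in section 3.1: H1.1 has no psychosocial covariate, and most of the named Aim 2 covariates can enter only through a between-race t test

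*Combined protocol and SAP*

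**What the plan says.** **Aim 1.** Section 3.1 asks whether %AF "is associated with SWS characteristics after controlling for psychosocial factors", and adds that "positive results would suggest that racial differences in SWS have genetic underpinnings". In section 9.3 the H1.1 models have seven covariates: each SWS characteristic "will be regressed on %AF controlling for age, sex, BMI, AHI, TST, sleep efficiency and WASO". None is psychosocial. A psychosocial term appears only in H1.2, which is specified as "including the best SWS predictor as dependent variable, the psychosocial factor as a classification factor", together with %AF and their product. Section 9.1 presents H1.2 as moderation: psychosocial factors "will partially moderate the above relationships".

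**Aim 2.** Section 3.1 states, without condition, control for two sets: "medial prefrontal (mPFC) atrophy, TST, AHI4% and cerebrovascular damage", and "psychosocial factors, health care behaviors and medical morbidity". The hierarchical model in section 9.3 has the matching factors in block 1 (including BMI, education and income), ApoE4 and ABCA7 in block 2, three imaging measures in block 3 and the SWS characteristic in block 4. Anything else, with psychosocial factors as the example, joins the final model only when an unequal-variance t test finds a significant difference between African-American and white participants. H3 follows the same plan.

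**Power.** Section 9.2 claims 80% power for an SWS measure explaining 3% of the variance "after adjusting for covariates that together explain at least 25% of the variance", with 200 complete participants.

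**The concern.** The two sections describe different estimates, and the analyst cannot follow both.

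In Aim 1 the omitted factor is the rival explanation that the protocol itself names. Section 2.1 reports perceived discrimination as partially associated with shorter SWS, and section 6.1 collects the Index of Race-Related Stress (IRRS) and the Perceived Stress Scale (PSS) for the purpose of control. A positive H1.1 result would be read as genetic although the model cannot separate ancestry from stressors that go with it.

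In Aim 2 the t-test rule asks whether a factor differs by race. For the SWA coefficient (hypothesis 2.2 and the 3%-of-variance power statement) the relevant question is whether the factor is related to both SWA and amyloid change. The two questions can have different answers. Section 2.1 concludes that the groups do not differ independently in sleep duration or OSA prevalence, so TST and AHI4%, both named in section 3.1, would probably be left out. H1.1 includes both.

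**Working it through.** **1. The plan's own power figure.** Inputs from section 9.2: N = 200, alpha 5%, 3% explained by the SWS measure, 25% by covariates. Effect size f² = 0.03/(1 − 0.25 − 0.03) = 0.0417. With noncentrality 200 × 0.0417 = 8.33 and one numerator df, power is 81.9%, which agrees with the stated 80%.

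**2. How often the t test admits a factor.** Splitting 200 completers in the ratio 150:60 gives 143 and 57. For a race difference of d SD the noncentrality is d × √(143 × 57/200) = 6.384d on 198 df (pooled approximation).

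| d (SD) | 0 | 0.2 | 0.3 | 0.4 | 0.6 |
|---|---|---|---|---|---|
| Chance of entry | 5% | 25% | 48% | 72% | 97% |

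**3. Aim 1, no direct %AF effect.** The documents give no correlations, so these are assumptions: a psychosocial factor correlates a with %AF and has standardized effect b on SWS. The induced correlation is ab. With n = 150 (Aim 1 concerns the African-American group), rejection is P(|Z + atanh(ab)√147| > 1.96). Adding the seven covariates and letting them explain part of the factor needs simulation (8,000 runs).

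| a/b | Shift | Formula, no overlap | Simulated, 30% overlap | Simulated, 50% overlap |
|---|---|---|---|---|
| 0.1/0.2 | 0.243 | 5.7% | 5.1% | 4.9% |
| 0.2/0.2 | 0.485 | 7.7% | 6.4% | 5.6% |
| 0.3/0.3 | 1.094 | 19.4% | 12.3% | 8.6% |

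With the factor in the model, rejection is 4.7-5.5%.

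**4. Aim 2, true SWA effect zero.** Simulation of 143 vs 57 with race, SWA, eight covariates and the t-test rule (6,000 runs and an earlier 8,000-run set; Monte Carlo error 0.3-0.5 points). Ranges cover race differences from 0.4 down to 0 SD.

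| Factor-SWA / factor-amyloid | No overlap | 30% overlap | 50% overlap |
|---|---|---|---|
| 0.1/0.2 | 5-6% | not run | not run |
| 0.2/0.2 | 6-9% | 5-7% | 5-6% |
| 0.3/0.3 | 10-23% | 7-15% | 6-10% |

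With the factor always in the model: 4.3-5.6%.

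Hand check at d = 0, 0.3/0.3, no overlap: atanh(0.09) × √(200 − 3 − 9) = 1.237, so rejection without the factor is 23.6%. The factor is omitted 95% of the time: 0.95 × 0.236 + 0.05 × 0.05 = 22.6%, against 22.3% and 22.9% simulated.

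**5. The other Aim 2 coefficients.** Race coefficient under the t-test rule: 4.6-6.4%, against 4.3-5.6% when always adjusted. Race-by-SWA interaction (3,000 runs per setting, 0.2/0.2 and 0.3/0.3, differences of 0 to 0.8 SD, confounder slope equal in both races): 4.6-5.5%.

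**6. Power cost of forcing covariates in.** Same f², going from 12 to 24 covariates: 81.9% throughout with N-based noncentrality. With residual-df noncentrality (186 × 0.0417 = 7.75, then 174 × 0.0417 = 7.25) power falls from 79.1% to 76.4%. If the 3% is the share before adjustment and the added factors correlate 0.3 with SWA, the unique share is 0.03 × (1 − 0.09) = 0.0273, and power at 24 covariates is 78.0% (N-based) or 72.2% (residual df).

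**The case against.** Five points weigh on the other side.

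- *Aim 1 does have a psychosocial term.* H1.2 contains one, and section 3.1 itself says social stressors may act as moderators. A reader might infer that Aim 1 is wholly unadjusted; that goes too far. What stands is that H1.2 covers one SWS measure and that, with the product in the model, its %AF coefficient is conditional on the level of the factor. It is not the adjusted association for each characteristic.
- *Aim 2 as worded concerns race and its interaction with SWS.* A reader might infer that the t-test rule distorts these. Step 5 does not support that. The harm is to the SWA main effect.
- *The rule works when races differ a lot.* At 0.6 SD the factor enters 97% of the time and SWA false positives are 4.5-6.1%. A large difference on a race-related stress index is plausible, though the documents give no figure. The higher rates apply to factors nearly balanced by race.
- *Design features already narrow confounding.* Block 1 holds education and income. The exclusions cover OSA, TST under 5 or over 10 hours, insulin-dependent diabetes, depressive symptoms, clinically relevant cardiac, pulmonary or endocrine disease, and listed drugs affecting cognition or SWS. They reduce confounding within the sample without removing it.
- *Forcing morbidity in can over-adjust.* Section 2.1 links hypertension and diabetes with reduced SWS, and the titles of the two works it cites there run from SWS to disease. Adjusting for these conditions could remove part of a real SWA effect. This stands, and it shapes the fix.

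**Conclusion.** The mismatch between sections 3.1 and 9.3 is certain from the text and should be fixed. Its numerical effect is conditional. Weak confounding does little. Moderate confounding (0.3/0.3) raises SWA false positives to 10-23% with no overlap and to 6-15% when modelled covariates explain 30-50% of the factor. The corresponding Aim 1 figures are about 19%, and 9-12% with overlap. All rest on assumed correlations, and the no-overlap figures are upper-end unless the correlations are read as partial. They illustrate sensitivity and do not estimate this study's error rate.

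Two stronger readings are not supported. The documents do not show that the race coefficient or the race-by-SWA test is compromised; both stay near 5% in the settings examined. Nor would a positive H1.1 result necessarily be a false positive. If a psychosocial factor lies downstream of ancestry, the coefficient without it is a total effect. What that coefficient cannot do alone is support the genetic interpretation.

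**What to change.** 1. **H1.1.** For every SWS characteristic, report the %AF coefficient without and with the collected psychosocial measures (IRRS, PSS). State that the genetic interpretation rests on the adjusted estimate.
2. **H2-3, sleep covariates.** Enter TST and AHI4% unconditionally, as section 3.1 says.
3. **H2-3, other covariates.** Replace the t-test rule with a prespecified list of named psychosocial and health-behavior measures (for example IRRS, PSS, SF36) and named morbidity variables. Report both the race and the SWA coefficients before and after these are added. Treat the morbidity-adjusted SWA estimate as a sensitivity analysis, because hypertension and diabetes may lie downstream of SWS.

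The cost is SAP wording on data already collected, plus some power. Section 9.2 should state the range from step 6: 81.9% unchanged on the N-based calculation, 79.1% to 76.4% on residual df, and as low as 72% if the added factors correlate 0.3 with SWA. That last figure is about 7 points below the 79.1% starting value and also below the 80% target.

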Brief Summary	African-Americans (AAs) have an increased prevalence of both Alzheimer's disease (AD) and vascular risk factors for AD such as diabetes and hypertension when compared to whites. However, in a recent community based study of non-demented elderly, black race was associated with higher amyloid burden after adjusting for vascular risk factors, suggesting the presence of additional physiological differences on AD-risk by race in the early stages of the disease. The purpose of this study is to test whether poor slow wave sleep (SWS) quantity (SWS duration) and quality (slow wave activity, SWA) is one of these physiological factors. To test these hypotheses, we will perform community outreach in barbershops, churches and senior centers in Brooklyn and other NYC boroughs with which we have created substantial ties in recent years. In consultation with community stakeholders, we will recruit 150 cognitively normal AA elderly (age 60-75) and 60 age, sex, BMI, income and education matched non-Hispanic whites from the same geographical areas. We will first perform a medical and cognitive evaluation (Visit 1). Participants will then undergo 2 nights of home sleep monitoring using an unattended device to exclude OSA, followed by 7 days of actigraphy with a sleep log to record sleep duration. Both devices will be returned by mail. Subjects with reported total sleep time (TST) between 5 and 10 hours and absence of moderate to severe OSA will be invited to perform a 2-night nocturnal polysomnography (NPSG) (Nights 1-2) and a PiB-PET MR scan (Visit 2).
Objectives	Objective 1: To test if African ancestry (%AF) is associated with short SWS duration and poor SWA in older AAs. Objective 2: To test the effect of race and its interaction with baseline short SWS duration/poor SWA on longitudinal amyloid deposition. Objective 3: To test the effect of race and baseline poor SWA on cognition. Secondary Objective 2.1: To test whether loss of sleep-dependent spatial navigational memory at baseline is a predictor of cognitive decline.
Methodology	30-36 month longitudinal study
Endpoint	Primary endpoint is longitudinal increase in amyloid deposition
Study Duration	5 years
Participant Duration	30-36 months

CONFIDENTIAL

[figure not shown]
This material is the property of the NYU School of Medicine and Langone Medical Center. Do not disclose or use except as authorized in writing by the study sponsor

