
Population
	
210 cognitively normal elderly (Clinical Dementia Rating [CDR]=0), self-identified as African-American (AA) or non-Hispanic white (NHW), ages 60 to 75 years, with English as their primary language. The reason for only including native English speakers is due to the nature of the study and cognition being one of the outcomes of the study. The reason for including only African American blacks and NHW is the focus of this grant which is on African Americans and their African genetic ancestry and admixture. Based on our preliminary data an existing literature, in order for genetic admixture analyses to be applied rigorously, the control group needs to be of NHW. The definition of NHW are people in the United States who are considered racially white and are not of Hispanophone identity or the Hispanosphere (terms used to refer to Spanish-language speakers and the Spanish-speaking world as compared to for example English-speaking of French-speaking to name a few). Other non-English non-Hispanic white ethnicities will not be invited to participate due to the lack of adequate neuropsychological tools and testers proficient in other native European languages and the confounding effects of immigration. These NHW participants will be located within the same zip codes as the AAs.

Study Sites
	
NYU locations: the Center for Brain Health (CBH) at NYULMC, the Center for Biomedical Imaging (CBI), NYU Langone Health, Department of Radiology, [name]
 
External Site: the Mount Sinai Integrative Sleep Center (MSISC) (New York, NY)

Number of participants
	
210 participants expected to be enrolled with 150 cognitively normal African-American elderly and 60 non-Hispanic white.

Statistical Analysis
	
We will incorporate standard techniques such as omnibus tests and appropriate adjustments to significance (α) levels (e.g., Bonferroni correction) for post-hoc contrasts to control for multiple comparisons. Both selection and attrition biases might occur. Appropriate techniques (e.g., Heckman 2-stage approach (GEE Probit Model) and Monte Carlo (EM algorithm) will be used to address biases or missing data. Since only two time points will be analyzed, we will use linear regression models with the annual rate of amyloid change as dependent variable. Significance will be defined by $p < .05$ where p will be Bonferroni corrected when testing post-hoc contrasts.

CONFIDENTIAL

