2.1 Background Information and Relevant Literature

Sleep duration in America has gradually declined over the last four decades, with current average sleep duration being of approximately 6 hours¹⁸. Parallel to this decline, African Americans (AAs) have the

CONFIDENTIAL

This material is the property of the NYU School of Medicine and Langone Medical Center. Do not disclose or use except as authorized in writing by the study sponsor

highest prevalence of long (≥ 9 h) and short sleep (≤ 6 h)⁶¹⁻⁶³, within the intervals commonly associated with morbidity and increased AD-risk⁶⁸⁻⁷⁰. AAs take longer to fall asleep¹⁸⁻²³, have lower sleep efficiency and have consistently shown to spend a smaller proportion of time in deep stages of non-REM (NREM) (also called slow wave sleep [SWS])^{19;20;23-28;32}. Possible mediators underlying these racial differences in sleep include age, sex, obesity, psychosocial factors, health care behaviors and medical disorders^{21;23;27;71-76}. A meta-analysis designed to estimate the magnitude of these variations in sleep, showed that racial/ethnic differences in sleep duration and continuity were moderated by the factors underlined above²³, while only psychosocial stressors (measured as perceived discrimination)^{20;21;26} were partially associated with the decreases in SWS duration, suggesting that race still remained an important independent risk factor for decreased SWS among AAs. A recent study confirmed this finding showing that decreased SWS duration was associated with an increased percentage of African ancestry (%AF)³⁹ even after adjusting for several demographic, socioeconomic and clinical covariates. Further replication is warranted, but African ancestry has also been associated to increased risk for hypertension⁷⁷ and diabetes⁷⁸ both of which have been linked with reductions in time spent in SWS^{79;80}.

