Self-identified AA and whites will be balanced by sex, age, BMI, income and education, and will live in the same NYC zip codes. Brooklyn will be the area of recruitment as it is the most ethnically diverse and largest most concentrated black population in the US -more than 900,000 blacks living in a 4-mile square area-. The sample will include self-identified African-American (AA) blacks and non-Hispanic whites. As described in our published methods^{158;166}, enrollment sites will include advertisements and collaborations with black-owned barbershops, beauty salons and churches that were part of our previous community studies in Brooklyn and other NYC boroughs. All advertisements and recruitment materials will be submitted for IRB approval prior to use. In addition, we will perform culturally-relevant educational events in senior centers and church health fairs. Recruitment will be implemented in consultation with a Community Activist ([name]) and a Community Advisory Board (CAB) that has been created for this cohort. It will include community stakeholders with whom we have long-standing relationships and consist of: black community leaders serving as Directors of Community-based organizations (CBOs) and members of the Brooklyn chapter of *CaringKind*. The CAB will comprise 8 members and will meet with the PIs and [name], who will be one of the lead members of the community advisory board every 2 months during year 1 and every 3 months thereafter. Once the award is made, it will discuss project goals, review recruitment strategies, refer individuals for participation and suggest new recruitment sites that might not have been available previously. Our success in assessing sleep in AAs is attributable to our sustained engagement efforts at the community level and help from former CABs.

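### H1.1 omits education and income, so a socioeconomic gradient in ancestry among African Americans could contribute to the %AF coefficient that Aim 1 would read as suggesting a genetic basis

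*Combined protocol and SAP*

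**What the plan says.** - **The H1.1 model.** Section 9.3 regresses each SWS measure on %AF, "controlling for age, sex, BMI, AHI, TST, sleep efficiency and WASO". The list is closed and has no socioeconomic or psychosocial term. H1.2 adds a psychosocial factor and its product with %AF, and names neither education nor income.
- **The H2-3 models.** The same section has these models "adjusting for the matching factors: age, sex, BMI, education and annual income (block 1". A further clause brings in other covariates that differ between African Americans and whites, but it belongs to H2-3 only.
- **Aim 1.** The Protocol Summary gives the objective as "To test if African ancestry (%AF) is associated with short SWS duration and poor SWA in older AAs". Section 3.1 says the test is whether %AF "is associated with SWS characteristics after controlling for psychosocial factors", and that "positive results would suggest that racial differences in SWS have genetic underpinnings".
- **Data collected.** Section 6.1 records annual household income alongside the stress and discrimination scales, so that outside influences on sleep can be controlled for. Years of education are also available, since the cognitive norms use them.
- **Balancing.** Section 4, under Study Enrollment, says "Self-identified AA and whites will be balanced by sex, age, BMI, income and education".
- **The earlier ancestry study.** Section 2.1 reports that its association held "even after adjusting for several demographic, socioeconomic and clinical covariates".

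**The concern.** The plan treats education and income as confounders when amyloid or cognition is the outcome, and says income is recorded to help control for disturbances of sleep. Yet the one model that has sleep as its outcome and ancestry as its exposure contains neither.

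Balancing does not fill the gap. It equalises income and education between the two groups. It cannot remove an association of %AF with income or education inside the African American group.

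If %AF is related to socioeconomic position (SES) among African Americans, and SES is related to SWS by routes that the seven covariates do not capture, then the %AF coefficient includes a non-genetic part. A positive Aim 1 result would then support the genetic reading in section 3.1 less well than it appears to. The psychosocial control promised for Aim 1 in section 3.1 is also missing from H1.1, where it might have absorbed some of this.

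**Working it through.** **1. The plan's own figure.** Section 9.2 claims 80% power at the 5% level for |r| = 0.20 in Aim 1. It does not state sidedness, so I assume two-sided. By Fisher z with k covariates, power ≈ Φ(atanh(r)·√(N−3−k) − 1.96).

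- N=200, k=0: atanh(0.20) = 0.2027 and √197 = 14.04, so the product is 2.846 and power is Φ(0.886) = 81.2%. This reproduces the plan's figure.
- N=150, k=0: 0.2027 × √147 = 2.458, so power is Φ(0.498) = 69.1%.

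The stated power therefore fits the 200 complete subjects assumed in section 9.2, while the aim is stated for African Americans, of whom 150 are planned ("210 participants expected to be enrolled with 150 cognitively normal African-American elderly and 60 non-Hispanic white"). The bias is worked at n=150 because that is where the gradient would act.

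**2. Induced correlation.** If %AF has no direct effect on SWS, the correlation produced by omitting SES is

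r(spurious) = r(%AF, SES) × r(SES, SWS).

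The documents give neither correlation. Both are assumed here, and both should be read as what is left after the seven H1.1 covariates.

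**3. Rejection rate at n=150 with the seven covariates.** Here √(150−3−7) = √140 = 11.83, and the rate is Φ(m−1.96) + Φ(−m−1.96) with m = atanh(r)·11.83.

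| Assumed correlations | Spurious r | m | Rejection rate |
|---|---|---|---|
| 0.1 × 0.1 | 0.01 | 0.118 | 5.2% |
| 0.2 × 0.2 | 0.04 | 0.474 | 7.6% |
| 0.3 × 0.3 | 0.09 | 1.068 | 18.7% |

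Simulated regressions (4,000 runs per setting, n=150) gave 7.9% for the second row and 20.2% for the third. With SES in the model the simulated rate was 5.0% and 5.9%. To create r = 0.20 with no direct effect, SES would need correlations of about √0.20 = 0.45 with both variables.

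**4. Why the same calculation does not carry over to the pooled sample.** If whites are included, most of the spread in %AF lies between the groups, where SES is balanced. Let p = 150/210 = 0.714. Suppose the correlation of %AF with SES within African Americans is 0.3, the SD of %AF is s in African Americans and about zero in whites, the gap between group means is d, and SES has SD 1 and equal means. Then

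pooled r = p·0.3·s / √(p·s² + p(1−p)·d²).

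The values of s and d are assumptions, not figures from the documents.

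- s=15, d=60: 3.21 / √(160.7 + 734.7) = 3.21/29.9 = 0.11.
- s=10, d=80: 2.14 / √(71.4 + 1306.1) = 2.14/37.1 = 0.06.

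Multiplied by an SES–SWS correlation of 0.3, the induced correlation is 0.017 to 0.032, against 0.09 within African Americans.

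**5. Cost of adjustment.** This is power at r = 0.20 when going from k=7 to k=9.

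- N=200: 79.8% to 79.4%.
- N=150: 67.0% to 66.3%.
- If SES and %AF correlate at an assumed 0.3, the effective r is 0.20 × √(1−0.09) = 0.191. Power with k=9 is then 75.4% at N=200 and 62.1% at N=150, which is 4.4 and 4.9 points below the seven-covariate model.

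**The case against.** **The background points to a small bias.** Section 2.1 says that only psychosocial stressors were partly associated with reduced SWS and that the ancestry association survived socioeconomic adjustment. The summary closing that section also reports SWS differences that remain after socioeconomic control. In addition, H1.1 already removes any SES effect that runs through BMI, AHI, TST, sleep efficiency or WASO. This stands, and it favours the lower rows of the table. But those background findings came from adjusted analyses, so they are a reason to make the adjustment here, not to omit it.

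**Income was probably meant as a control.** Sections 3.1 and 6.1 read together suggest so. That is fair for income, and the defect is then that section 9.3 does not carry out a stated intention. Education is not in the section 6.1 list of added control variables.

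**Income or education may lie on the path from ancestry to sleep.** Adjustment would then remove part of a real association. That part is not the genetic effect of interest, and reporting both models keeps it visible.

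**Stronger readings that the documents do not support.**

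- A reader might infer that the false-positive rate is worse with 200 subjects because the test is more precise. That applies a within-group gradient to a pooled sample whose SES is balanced between groups. No n=200 rejection rate should be quoted.
- A reader might infer that H1.1 is a weaker test than the cited ancestry study. Section 2.1 does not list that study's full covariate set, so one can say only that it reportedly had socioeconomic covariates and H1.1 has none.
- A reader might infer that adding two covariates would justify a genetic conclusion. It would not, because discrimination and other exposures related to ancestry remain outside H1.1.

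**Conclusion.** The point holds as a gap in the model. H1.1 has no education or income term, no clause in section 9.3 adds one, and between-group balancing cannot deal with a gradient inside the African American group. Such a gradient could contribute to the %AF coefficient.

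Its size is unknown. At n=150 the illustrative rejection rate runs from about 5% to 19% as both assumed correlations go from 0.1 to 0.3, and the documents' own background favours the lower part of that range. This is a risk to the interpretation of Aim 1, not evidence that a positive result would be spurious. The wording in section 3.1 is itself hedged. The change is worth making because it is cheap and bears on what a primary aim can claim.

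**What to change.** In section 9.3:

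1. Add education and annual income to the H1.1 covariates and carry them into H1.2.
2. Report the %AF coefficient with and without them.
3. State that the adjusted model is the minimum basis for interpreting Aim 1, and that residual non-genetic confounding remains possible even then.

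Both variables are already collected, so the change is a line or two of text and about 2 degrees of freedom. It costs under 1 point of power at r = 0.20, or about 4 to 5 points if SES and %AF correlate at an assumed 0.3, which is also the situation in which the unadjusted model is most exposed to bias. Any part of the %AF association that runs through income or education drops out of the adjusted coefficient, and the unadjusted model reported beside it shows how much.
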